4.4.2 Data Collection and Follow-up for Withdrawn Participants

In the case of withdrawal, every attempt will be made to obtain consent to continue to follow patients for the occurrence of mortality, hospitalizations, and other safety signals via telephone or in-person contact with participants, relatives, and dialysis unit staff and records. As a last resort, the social security death index will be queried for mortality events on individuals otherwise lost to follow-up.

Participants will be deemed as lost to follow-up after ≥ 3 attempts have been made to contact the patient via their preferred means of contact (telephone or email), ≥ 1 attempt has been made to contact the patient via their secondary means of contact, and ≥ 1 attempt to contact next of kin is unanswered.

For withdrawn participants not withdrawing consent, attempts will be made to obtain endpoint TDI echocardiograms and PET CFR according to the original study in order to preserve the intention to treat analysis. PET scans will not be obtained in the event of withdrawal/termination due to pregnancy.

5 Study Drug

5.1 Description

Study drugs will be administered as matched, gel-coated capsules containing ISD (10, 20 or 40 mg), HY (10, 35, or 75 mg), or placebo (methylcellulose powder).

5.2 Treatment Regimen

As depicted in Figure 4, 16 participants will be randomized in a 1:1 fashion to either placebo 3x daily or ISD/HY 10 mg/10 mg, 3x daily for 1 week. Doses scheduled to be administered within 2 hours prior to a dialysis session will be held and administered post-dialysis on dialysis days. Participants will be contacted by phone or in person to review tolerability and adverse events at 1 week after drug initiation and will be examined in person at 2 weeks. Dialysis records will be reviewed for hypotension at each visit. The sequence will be repeated following the scheduled dose titration which will occur following the 2-week visit. Adjustment to dosage of concomitant medications, the dialysis prescription, or the study drug on the basis of hypotension will occur as described in Section 6.7.

All randomized participants will receive an initial one-week supply of study medication following the baseline visit, and a one-week supply after the Week 1 visit. Those assigned to ISD/HY will begin treatment at 10/10 mg 3X daily. Participants randomized to placebo will follow the identical schedule. Participants will be contacted at 1 week to check for the occurrence of adverse events and dose-limiting symptoms, and those tolerating the study drug will have the dose increased to ISD/HY 20/35 mg 3X daily or placebo. At Week 2 participants will be examined in-person at their dialysis units. Adverse events will be reviewed and dialysis run sheets will be examined for the occurrence of inter- or intra-dialytic hypotension at each visit. In the absence of dose-limiting hypotension or other adverse events, the dose of ISD/HY will be increased to 40/75 mg 3X/daily following the Week 2 visit.

During the 4-week dose escalation phase, a study drug request form will be entered into the data management system at 1 week, 2 weeks and 4 weeks to request the next supply of study drug. Unless there is a contraindication to a dose increase (e.g. hypotension), the investigator will indicate approval for dose escalation on the request form. The Data Management System will generate a unique kit number based on the randomized treatment assignment and the prior dose. If up-titration to the next dose is contraindicated, the Clinical Center investigator will indicate this on the study drug request form and a kit number corresponding to the current dose of will be generated.

If down-titration of the study drug dose is required during the dose escalation phase or during the treatment phase, the Clinical Center investigator will request a dose reduction on the study drug request form. In this case, a supply of blinded study medication using the next lower dose of ISD/HY or placebo will be provided. In the event that a participant is already receiving the lowest dose, study medication will be discontinued. In the event that a 3rd down titration of dose is required study medications will also be discontinued. Un-blinding to preserve patient safety will be considered via a formal request to the DCC.

If the dose escalation schedule is interrupted (e.g., if a participant is hospitalized at the scheduled time of dose escalation and did not take study drug during the hospitalization), dose escalation will be delayed until the participant has had access to the current dose of study drug for the specified interval (1 week for the first dose level, 2 weeks for the second dose interval). If, due to a considerable delay in dose escalation, a participant has not reached the final dose assignment by their Week 8 visit, the participant will remain at the current dose of study drug for the remainder of the study and the treatment phase will be shortened accordingly such that the total duration of study participation is not increased as a result of the delay. For example, if dose escalation is not completed until week 10, the treatment phase will be 16 weeks rather than 22 weeks.

Participants will be contacted by phone or in person at Weeks 1 and 3 (plus or minus 3-5 days) as described above and will be examined in-person at Weeks 2 and 4. Dialysis records will be reviewed at each time point. Following the Week 4 visit a 12-week supply of the maximal tolerated dose of study medication will be distributed to participants who will be evaluated in-person at the dialysis unit every 4 weeks for the duration of the study. A 10-week supply of study medication will be distributed to participants following the Week 16 visit. At Week 26, participants will have a close-out visit, echocardiography and PET scan at the medical center and will then discontinue study medications.

In the event of dose-limiting symptoms such as headache, hypotension or gastrointestinal distress, dose increases will be deferred until symptoms have resolved and there has been adjustment to concomitant therapies, diet or dialysis prescription as described in Section 6.7, the dose of study medication or matched placebo may be reduced as applicable. During both the dose escalation phase and the treatment phase, the dose may be reduced to the next lower dose level in the event of adverse events as described in Section 6.7. In order to maintain the blind, all participants will receive blinded medication supplies according to the specified dose within 3 days of the Week 1, Week 2 and Week 4 visits, and within 1 week of the Week 16 week visit, regardless of whether the dose is changed.

Method for Assigning Participants to Treatment Groups

The randomization schedule will be stratified by left ventricular ejection fraction (LVEF) at $\leq 45\%$ vs $> 45\%$ to ensure balance across treatment arms of patients with preserved versus reduced LVEF. A clinical echocardiogram will be used for LVEF determination if available within 6 months. If no echocardiogram is available within the required timeframe then a study cardiologist will perform a limited reading on the study echocardiogram done during the baseline visit. There may be a delay of up to 72 hours between the baseline visit and randomization to allow for the completion of this limited reading.

Randomly permuted blocks of random sizes will be used to control the balance of participants assigned to each treatment regimen within each stratum. This method guarantees that at no time during randomization will the number of participants in any arm be grossly imbalanced, and ensures that the investigator will be unable to predict assignments. All randomization schedules will remain confidential, and known only to authorized members of the central pharmacy.

All relevant screening and eligibility confirmation data must be entered into the data management system in advance of randomization, in order for an eligible participant to be randomized. When the study team agrees that all eligibility criteria have been met, the patient will be randomized according to the pre-prepared, stratum specific randomization schedule. This randomization process will provide a randomized treatment assignment for that participant within the relevant stratum, linked with a specific drug kit/box prepared at the study pharmacy. The kit will then be provided to the investigative team for distribution at the randomization/baseline visit.

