6.7 Hypotension Procedures

In the event of recurrent intra-dialytic hypotension or serious hypotension not attributable to acute events (e.g. acute myocardial infarction, sepsis), the investigator will review the participant's non-study anti-hypertensive medications, dry weight, and volume status. The participant's clinician will be contacted to consider the following interventions listed in the preferred order of implementation:

- 1) Decrease non-study anti-hypertensive medication(s)
- 2) Increase dry weight if there is no evidence of peripheral or pulmonary edema
- 3) Reduce ultrafiltration rate by increasing dialysis session duration
- 4) Reduce dose of study medication if:
 - a. Peripheral or pulmonary edema is present
AND
 - b. There are no other anti-hypertensive medications prescribed OR other anti-hypertensive medications should not be discontinued (e.g., beta blocker following myocardial infarction)
- 5) Discontinue study medication when reduction below minimal dose is required

Treating clinicians will be free to manage hypotension according to standard clinical practices and are not obligated to follow the study guidelines with respect to non-study medication, fluid removal rate, or dry weight. In contrast, dose reduction or discontinuation of study drug will be directly managed by study staff in accordance with the guideline. All enrolled participants will continue to be followed for the occurrence of adverse events and for end of study cardiac testing regardless of whether study medications are discontinued.

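### Section 6.7 has no step to a lower study-drug dose when hypotension persists without edema, although Sections 3.1 and 5.2 permit a reduction

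*Combined protocol and SAP*

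**What the plan says.** Two sentences in Section 5.2 send the reader to 6.7. One says that adjustments to "the study drug on the basis of hypotension will occur as described in Section 6.7". The other, covering both the escalation and the treatment phase, says that "the dose may be reduced to the next lower dose level in the event of adverse events as described in Section 6.7". Section 6.4 likewise defers to the procedures that follow it.

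Section 6.7 is triggered by recurrent intra-dialytic hypotension or by serious hypotension without an acute cause. It lists five measures in a preferred order:

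1. Lower the other antihypertensives.
2. "Increase dry weight if there is no evidence of peripheral or pulmonary edema".
3. Lower the ultrafiltration rate by lengthening the session.
4. Reduce study drug if two conditions joined by AND are met: (a) "Peripheral or pulmonary edema is present"; (b) "There are no other anti-hypertensive medications prescribed OR other anti-hypertensive medications should not be discontinued".
5. "Discontinue study medication when reduction below minimal dose is required".

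The section then separates responsibilities. Treating clinicians are "not obligated to follow the study guidelines with respect to non-study medication, fluid removal rate, or dry weight". By contrast, "dose reduction or discontinuation of study drug will be directly managed by study staff in accordance with the guideline".

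Section 3.1 is broader. For poor tolerance or a drug-related adverse event, with hypotension given as an example, study drug may be held or reduced, down to 10/10 mg three times daily. It sets no edema condition. A sentence late in 5.2 also lists hypotension among dose-limiting symptoms and allows reduction as applicable, after mentioning the 6.7 adjustments to other treatment.

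**The concern.** Steps 1 to 3 are in the treating clinician's hands and may be refused or may not work. The study-drug steps are in the study staff's hands and are tied to the guideline. If the first group of measures runs out and edema is absent, the guideline offers staff nothing further for a participant above the lowest dose. Read literally, the participant stays on the current dose of a vasodilator combination until edema develops.

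The first thing at stake is safety. Section 1.4 names symptomatic hypotension, particularly during dialysis, among the main risks of both drugs, and states that the combination has not previously been tested in a trial of patients on chronic hemodialysis. The second is consistent conduct. Tolerability is a primary objective, and Section 3.2.2 counts any reduction or discontinuation of study drug as a failure. Two participants with the same clinical course could be classified differently because one was managed under 6.7 and the other under 3.1.

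**Working it through.** The plan states no figure on this point. The check treats 6.7 as a decision rule and compares it with the other sections.

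**Starting point.** The participant is on 20/35 or 40/75 mg three times daily and meets the 6.7 trigger. Steps 1 to 3 have failed, are not possible, or have been declined. Step 5 does not apply, because the next level down is not below the minimal dose. Only step 4 remains.

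**Inputs to step 4.** Edema is present or absent (2 states). Other antihypertensives are not prescribed, should not be discontinued, or could be stopped but are kept by the clinician (3 states). That gives 2 × 3 = 6 combinations.

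| Edema | Other antihypertensives | 4a | 4b | Step to a lower dose in 6.7? |
|---|---|---|---|---|
| Yes | None | met | met | Yes |
| Yes | Should not be discontinued | met | met | Yes |
| Yes | Could be stopped, but kept | met | arguable | Arguable |
| No | None | not met | met | No |
| No | Should not be discontinued | not met | met | No |
| No | Could be stopped, but kept | not met | arguable | No |

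Two are covered, three are clearly uncovered and one is arguable: 2 + 3 + 1 = 6. The three uncovered combinations are exactly those without edema; 4a fails there whatever the answer to 4b.

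**Clearest case.** No edema and no other antihypertensive. Step 1 is empty and steps 2 and 3 can fail or be declined, so study drug is the only antihypertensive left to lower. The eligibility criteria admit such a person: Sections 4.1 and 4.2 do not require background antihypertensive treatment, and exclusion q lets patients stop prior ISD or HY in order to enroll.

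**The same participant under other sections.**
- 3.1: hold or reduce, at discretion.
- 5.2, late sentence: reduce as applicable. The sentence after it points back to 6.7.
- 5.2 and 5.3, drug supply text: describe how a lower dose is requested and dispensed once needed, but give no criterion for needing it.
- 4.4.1: gives recurrent hypotension on the lowest dose as an example of intolerance leading to withdrawal, which presupposes that a step-down has already happened.
- 6.8: covers headache and gastrointestinal symptoms, not hypotension.

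Section 6.7 itself contains no hold.

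**Dose at stake for one participant at full dose.** Staying put means 3 × 40 = 120 mg ISD and 3 × 75 = 225 mg HY per day. One level down, the 5.2 rule, is 3 × 20 = 60 mg and 3 × 35 = 105 mg. The floor in 3.1 is 3 × 10 = 30 mg of each.

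**The case against.** The strongest reply is that permission to reduce already exists. Section 3.1 gives it, 5.2 gives it in general terms, 5.3 allows for down-titration at any time, and 1.4 says that reductions for intolerance are provided for. On this view investigator judgment is the intended mechanism. The 6.7 list is offered for consideration in a preferred order, and step 4 says *if*, not *only if*. This stands to the extent that a reader who infers that 6.7 forbids reduction without edema goes too far. It does not remove the inconsistency: the preferred order concerns what the clinician is asked to consider, while 6.7 separately ties study-drug reduction to the guideline and 5.2 names 6.7 as the place where the rule is found.

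A second reply is that the edema condition is deliberate. Without edema, dry weight can be raised until blood pressure recovers or edema appears, and then 4a is met. That is a sensible first measure and should stay. But it needs a clinician willing to do it, and otherwise makes volume overload the route to a lower vasodilator dose.

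A third concerns size. A reader might count four of the six combinations as uncovered. The documents do not support that, because a clinician's decision to keep a drug can be read as a judgment that it should not be discontinued; the post-infarction beta blocker in 4b is only an example. A reader might also measure the impact by one participant's share of an arm of 8, or by the change in the Table 1 confidence limits from zero to one event. Any single event has that effect in an arm of 8, so neither figure measures this gap. Nor is anyone counted twice: each participant has one actual course, and Section 3.2.1 still records the hypotension as a safety endpoint.

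**Conclusion.** The point holds as an incomplete safety rule in 6.7 that does not agree with 3.1 and the general wording in 5.2. It covers participants above the lowest dose with recurrent or serious hypotension and no edema, after steps 1 to 3 are exhausted or declined.

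The group is narrow. Entry requires pre-dialysis systolic pressures of at least 120 mm Hg and excludes recent recurrent intra-dialytic hypotension, and several measures come before step 4. The documents give no frequency; the three uncovered combinations are logical cases, not rates. The conclusion assumes that study staff follow 6.7 as written, as that section directs. If they rely on 3.1 instead, the participant is protected, but reductions then depend on which section is used.

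No sample-size or power figure is affected. This is a cheap improvement for patient safety and for consistent application of reductions that count as tolerability failures.

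**What to change.** Keep the preferred order of steps 1 to 3 and add an alternative to 6.7 step 4: *OR recurrent or serious hypotension persists after steps 1-3 were tried, declined by the treating clinician or not possible, with or without edema: hold or reduce study drug by one dose level.* Make 3.1, 5.2 and 6.4 refer to this single rule. The clause also settles the arguable combination of edema with a kept antihypertensive.

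The cost is a short protocol amendment. The study drug request form in 5.2 already handles reductions, so no new data item is needed. The downside is a few more dose reductions, which would slightly lower the mean dose and might weaken the contrast in E' and CFR.

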5.3 Preparation and Administration of Study Drug and Maintenance of Blind

Study drug and matching controls will be prepared by the Investigational Drug Service (IDS). The IDS will distribute study drug kits, containing a 1-week supply at baseline and Week 1, a 2-week supply at Week 2, a 12-week supply at Week 4, and a 10-week supply at Week 16. Drug supplies will be packaged to contain a 3-day or 5-day supply of extra medication depending on the visit interval.

All doses of ISD, HY, and placebo will be manufactured to have identical appearances using gelatin encapsulation or equivalent methods. IDS personnel responsible for preparation of study drug will not have access to study data or results and will not participate in analyses of study data or publications. However, appropriate IDS personnel will have access to the randomization scheme and code in order to prepare study drug kits containing the correct dose of active medication or placebo for each group and study participant.

During the dose titration phase, IDS personnel will prepare kits containing a 10-day supply of the specified dose of ISD/HY or matched placebo for each group at baseline and Week 1. These packages will be replaced with kits containing a 2-week + 5 day supply of the next dose of study drug or placebo following the Week 2 visit, a 12-week + 5 day supply following the Week 4 visit, and a 10-week + 5 day supply following the Week 16 visit. If up-titration to the next dose is not indicated (e.g. due to hypotension or gastrointestinal symptoms), the investigator will notify the IDS, and a package containing

the last dose of ISD/HY or placebo will be substituted. If at any time, the participant experiences dose-limiting symptoms requiring down-titration of study drug, the IDS will be notified to prepare a new supply of study drug at the next lowest dose for the appropriate number of days remaining until the next scheduled drug distribution. The participants will be instructed to discontinue study medication until they receive the new package.

The investigator will notify the IDS when down-titration of dose is required for a particular participant. In this case, the IDS will prepare a supply of blinded study medication using the next lower dose. In the event that a participant is already receiving the lowest dose, placebo will be substituted. As only 3 dose-level of medications are specified, study medications will be discontinued in the event that a down titration below the lowest dose of study medications is required. Un-blinding to preserve patient safety will be allowed after formal documentation of the need by the investigator and a formal request to the IDS.

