6.4 Week 1, 2, 3, 4, 8, 12, 16, 20, 24 Visits

Participants will be contacted by telephone or in-person at the dialysis unit 1 week after the start of study medications for the occurrence of adverse events (hypotension, headache, gastrointestinal symptoms, and hospitalizations). Those participants tolerating study medication will have the dose increased to ISD/HY 20/35 mg or placebo for the next week. Dialysis treatment records will be reviewed for the occurrence of hypotension and standard of care dialysis labs will be reviewed at each visit. The dose of study drug may be reduced if a participant experiences dose-limiting adverse events, as outlined below.

Participants will be interviewed in-person at the dialysis unit at Week 2, Week 4 and Week 16 for the occurrence of adverse events (intra-dialytic hypotension, headache, gastrointestinal symptoms, and hospitalizations). Dialysis treatment records will be reviewed for the occurrence of hypotension and standard of care dialysis labs will be reviewed. Vital signs and edema will be assessed. In the absence of dose-limiting symptoms, the dose of study medications will be increased following the Week 2 visit. The dose of study drug may be reduced if a participant experiences dose-limiting adverse events, as outlined below. Following each visit, the appropriate dose of study drug will be delivered to study participants. At that time, pill containers will be returned and unused pills counted and destroyed. Participants will be contacted at Week 3 to collect adverse event information.

Following the Week 4 visit, participants will be contacted in-person or by telephone every 4 weeks at their dialysis facilities. Adverse events and tolerability will be reviewed. Dialysis treatment records will be analyzed for the occurrence of hypotension and standard of care dialysis labs will be reviewed. Pill containers will be returned and unused pills counted and destroyed after the Week 16 visit.

The IDS will be notified to proceed with refill of study medication for patients continuing in the study following the Week 1, 2, 4, and 16 visits.

Visit windows will be \pm 3 days for the week 1, 2 and 4 visits and \pm 7 days for week 8-30 visits.

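### The 5 spare days in the Week 4 and Week 16 kits do not cover the plan's own visit and delivery windows, so a fully adherent, in-window participant can run out of study drug

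*Combined protocol and SAP*

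**What the plan says.** **Supply.** Section 5.3 packs "a 12-week + 5 day supply following the Week 4 visit, and a 10-week + 5 day supply following the Week 16 visit". The baseline and Week 1 kits hold 10 days each, and the Week 2 kit holds 2 weeks plus 5 days. The stated principle is: "Drug supplies will be packaged to contain a 3-day or 5-day supply of extra medication depending on the visit interval".

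**Visit windows.** Section 6.4 allows plus or minus "3 days for the week 1, 2 and 4 visits" and plus or minus "7 days for week 8-30 visits". The schedule in section 15 differs in two places: Week 1 is confined to days 6 to 8, and Week 26 may move 2 weeks either way.

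**Delivery.** Section 3.1 has kits arrive within 1 day of the Week 1, 2, 4 and 16 visits, with up to 3 days tolerated. Section 5.2 allows 3 days for Weeks 1, 2 and 4, but for Week 16 says "and within 1 week of the Week 16 week visit, regardless of whether the dose is changed".

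**No carry-over, no top-up.** Section 6.4 states: "Pill containers will be returned and unused pills counted and destroyed after the Week 16 visit". It triggers refills only after Weeks 1, 2, 4 and 16. The only as-needed distribution in the section 15 schedule is at Week 3.

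**End of treatment.** The Study Summary gives 26 weeks of administration. Section 5.2 has participants attend at Week 26 for a close-out visit, "echocardiography and PET scan at the medical center and will then discontinue study medications".

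**The concern.** The spare supply is evidently meant to absorb slippage between visits, but it is smaller than the slippage the plan permits. A participant who takes every capsule and keeps every appointment inside its window can be without drug for some days around Week 16, or just before the Week 26 echo and PET.

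The second case deserves more attention. E' and CFR each have one follow-up measurement, at Week 26, with 8 participants per arm. Section 1.2 gives half-lives of about 1 hour for isosorbide dinitrate and about 5 hours for its 5-mononitrate, so a gap of several days means imaging off drug, while section 5.2 intends treatment to run up to imaging. Section 6.5 allows the Week 26 visit to be split in two, so echo and PET could also fall at different intervals from the last dose. Neither section 6.5 nor the schedule lists the date of that dose as an item to record.

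**Working it through.** **Assumptions.** Day 0 is baseline; Week 4, 16 and 26 are days 28, 112 and 182; windows are counted from those days; every dose is taken; leftovers are not carried over.

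**The plan's own total.** 1 + 1 + 2 + 12 + 10 = 26 weeks = 182 days, which agrees with the stated duration. On nominal dates there is no gap.

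**Formula.** A kit of K days given on day s covers days s to s + K − 1. Full days without drug before day v (imaging or next kit) = max(0, v − s − K).

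**Week 16 kit to imaging.** K = 70 + 5 = 75. Given on day 112 it ends on day 186; given on day 105 (7 days early) it ends on day 179.

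| Imaging day | Kit on day 112 | Kit on day 105 |
|---|---|---|
| 182 (nominal) | 0 | 182 − 105 − 75 = 2 |
| 189 (+7 days, 6.4) | 189 − 112 − 75 = 2 | 9 |
| 196 (+14 days, section 15) | 9 | 16 |

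**Week 4 kit to Week 16 kit.** K = 84 + 5 = 89. Given on day 28 it ends on day 116; given on day 25 it ends on day 113. The latest Week 16 visit is day 119.

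| Week 16 delivery | Next kit on day | Week 4 kit on day 28 | Week 4 kit on day 25 |
|---|---|---|---|
| Same day | 119 | 119 − 28 − 89 = 2 | 5 |
| 3 days later (3.1) | 122 | 5 | 8 |
| 7 days later (5.2) | 126 | 9 | 12 |

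**Baseline kit.** K = 10, ending on day 9. With Week 1 on day 8 (section 15) and 3-day delivery, the next kit comes on day 11: 11 − 0 − 10 = 1 day short. With Week 1 on day 10 (6.4), it comes on day 13: 3 days short.

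**Size of the mismatch.** This is the number of spare days needed to span every in-window schedule, against the 5 provided.
- Narrow reading (3-day delivery, 7-day Week 26 window): Week 4 kit 122 − 25 − 84 = 13; Week 16 kit 189 − 105 − 70 = 14.
- Wide reading (7-day delivery, 2-week Week 26 window): 126 − 25 − 84 = 17; 196 − 105 − 70 = 21.

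**Sensitivity.** If leftovers were kept, contrary to 6.4, the two kits would give 89 + 75 = 164 days from day 28, ending on day 191. That covers day 189 but leaves 196 − 1 − 191 = 4 days at day 196.

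**The case against.** **Nothing goes wrong on nominal dates or with ordinary adherence.** This stands. At 90% adherence the 75-day kit lasts 75/0.9 ≈ 83 days, and at 75% it lasts 100. The gap needs near-full adherence plus a visit or delivery more than 5 days late, or an early preceding kit. The right wording is that participants can run out.

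**A reader might infer that 20% or 31% of participants would reach imaging without drug.** Those are shares of permitted date pairs under same-day Week 16 delivery: 45/225 with the 7-day Week 26 window and 135/435 with the 2-week window. They treat every date as equally likely. A later kit also lasts later: a 3-day delivery lag gives 21/225 (9%) and 91/435 (21%), and a 7-day lag gives 3/225 (1%) and 45/435 (10%). None is a risk estimate. The worst mid-study gap (Week 16 kit on day 126) and the worst pre-imaging gap (kit on day 105) cannot occur in the same participant.

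**A reader might infer, from the short half-lives, that the drug-placebo difference is diluted.** Section 6.9.2 already withholds nitrates for 24 hours before PET, so a fully supplied participant also comes to the CFR scan without recent nitrate. Hydralazine is not named there, and section 6.9.1 states no such hold for echo. Section 3.2.3 treats E' and CFR as surrogates for fibrosis and for microvascular structure and function. Nothing in the documents shows whether they would change over 2 to 16 days off drug.

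**A reader might also infer that the adherence measure would hide the gap.** Sections 5.4 and 7.3 define adherence against prescribed doses, so visit dates and pill counts could reveal it.

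**The stated 26 weeks might be a cap, making drug-free days before late imaging intentional.** Section 5.2 points the other way, and the two need reconciling. A kit given on day 105 ends on day 179 and falls short of day 182 on either reading.

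**Conclusion.** The mismatch is real and holds on the narrowest reading: 5 spare days against a 7-day visit window leaves 2 days uncovered even with same-day delivery and an on-time preceding kit. In the worst permitted cases the gap before imaging reaches 9 days under section 6.4 and 16 under section 15. The gap around Week 16 reaches 8 days under the delivery rule in 3.1 and 12 under that in 5.2, in both cases with an early Week 4 kit.

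The day counts are firm given the assumptions listed. The documents support neither a predicted frequency nor a claim that E' or CFR would be biased by any stated amount. This is a cheap improvement to supply logistics, not a defect that undermines the endpoints.

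**What to change.** 1. Reconcile the passages that disagree: the Week 26 window (6.4 against section 15), the Week 16 delivery window (3.1 against 5.2), the Week 1 window (6.4 against section 15), and the 26-week duration in the Study Summary with 5.2, which continues drug up to imaging. Days 189 and 196 lie beyond 26 weeks, so how long treatment may run is for the sponsor and investigator to settle; this review does not choose.
2. Then make the spare supply agree with the visit and delivery windows for every kit, either by enlarging kits or by narrowing windows, so that no in-window schedule leaves a participant without drug.
3. Record the date of the last dose before the Week 26 echo and before the PET, separately if the visit is split.

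The cost is some extra capsules of generic drug and placebo for 16 participants and a change to the pharmacy instructions, plus one data item. The downside is slightly more unused drug to count and destroy, or tighter scheduling.
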